2. INTRODUCTION AND RATIONALE

Left-sided surgical acute colonic diseases (perforated diverticulitis with generalized peritonitis, colon perforation, large bowel obstruction, colon cancer perforation or obstruction, ischemic colitis, abdominal trauma) are still a life-threatening condition requiring urgent surgical intervention.

Despite several published randomized trials, showing that primary anastomosis with or without protective ileostomy is feasible and randomized trials for laparoscopic lavage with conflicting results, the Hartmann's procedure, described for the first time in 1921 as an alternative to abdominoperineal resection for the treatment of upper rectal tumours, is still performed in many hospitals worldwide. Hartmann's procedure is the surgical resection of the rectosigmoid colon with closure of the anorectal stump and formation of an end colostomy. It remained the most common procedure for acute diverticulitis and colonic perforation in emergency setting for many years. Hartmann's procedure is safe for severely ill patients; however,

GOODBYE HARTMANN – AFTER 100 YEARS HARTMANN'S PROCEDURE IS GOING TO BE ABANDONED?

STUDY PROTOCOL WITH ICF - VERSION 2 09.03.2021

restoring intestinal continuity for such patients is often associated with high morbidity leaving a great percentage of patients with (up to 50%) with a permanent stoma. [1]

Hartmann procedure' is a rapid and simple surgical technique intended to decrease perioperative morbidity and mortality. This technique is often performed by young surgeons. Indeed, end-colostomy may be necessary in situations where restoration of continuity is risky, either because of unfavourable local conditions (Hinchey IV peritonitis) or because a more definitive resection must be aborted due to hemodynamic instability. Although anastomosis at the time of surgery is an alternative approach to Hartmann's procedure, there have been concerns about the safety of this approach.

In the last decade the Hartmann's procedure has been revalued and the results of different studies [DIVA arm of the LADIES trial (the fourth and largest randomized clinical trial to date to compare Hartmann's procedure with primary resection and anastomosis in patients with perforated diverticulitis with purulent or and fecal peritonitis); DIVERTI study; Halim et Al] showed that more patients in the primary anastomosis group were stoma free compared with patients in the Hartmann's procedure group. [2,3,4]

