Several studies have observed no differences in major postoperative complications or postoperative mortality between patients undergoing primary anastomosis versus Hartmann's procedure. Hartmann's procedure reversals were associated with a higher risk of serious postoperative complications than were stoma reversals after protected primary anastomosis. [2-7]

The management of colorectal cancer emergencies is challenging. WSES guidelines recommend in case of perforation resection with anastomosis, with or without ileostomy. Hartmann's procedure should be preferred to simple colostomy, since colostomy appears to be associated with longer overall hospital stay and need for multiple operations, without a reduction in perioperative morbidity in patients with colorectal cancer obstruction. Resection with primary anastomosis should be preferred for uncomplicated malignant left-sided large bowel obstruction in absence of other risk factors. Patients with high surgical risk are better managed with Hartmann's procedure. Despite the growing evidence in favour of primary anastomosis and its inclusion as a valid treatment option for perforated diverticulitis or perforated sigmoid colon cancer in recent clinical practice guidelines, surgeons have been reluctant to perform anastomosis. Moreover, the postoperative course of the septic patient is unpredictable and it very hard to estimate it intraoperatively.

In the setting of purulent or fecal contamination most surgeons choose Hartmann's procedure to eliminate also legal concerns about anastomotic leakage. It's important to note that most of these procedures are performed off normal working hours when maybe best colorectal expertise is lacking for decision making regarding anastomosis. [8-10]

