3. STUDY OBJECTIVES

- To evaluate the role of Hartmann's procedure in emergency setting for left-sided colonic acute surgical disease (perforated diverticulitis with purulent or fecal peritonitis; colon cancer perforation-occlusion; ischemic colitis; abdominal trauma) and the type of surgery commonly performed in different level of care hospitals.
- To investigate which factors contribute in the choice of Hartmann's procedure instead of colon resection with primary anastomosis (Hospital characteristics, surgeon experience, time of surgery, age of patients, comorbidities, etc)

GOODBYE HARTMANN – AFTER 100 YEARS HARTMANN’S PROCEDURE IS GOING TO BE ABANDONED?

STUDY PROTOCOL WITH ICF - VERSION 2 09.03.2021

- To evaluate postoperative course and complications rate (Length of stay, complication, reoperation) of different surgical procedures.

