5.4 SAMPLE SIZE CALCULATION

The data will be used to investigate the specific characteristics to choose Hartmann's procedure versus primary anastomosis for left-sided acute surgical colonic diseases. Based on literature findings it has been estimated that, on average, three patients will undergo urgent left-sided colonic diseases resection per month at each participating centre. Applying root mean square percentage error (rMSPE) of 15%, 500 patients treated with left colon resection with or without primary anastomosis should be included.

Inclusion of 500 patients will be sufficient to analyze primary study objective 1 and primary study objective 2. Therefore, the aim is to include at least 500 patients.

METHODS

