5.7 LIST OF STUDY PARAMETERS

- Etiology: perforated diverticulitis; perforated colonic cancer; large bowel perforation-obstruction; colon cancer perforation-obstruction; colon ischemia; abdominal trauma.
- Hospital Characteristics: hospital type (academic, non-academic teaching, categorical, secondary hospital, tertiary hospital, level 4- trauma center); annual volume of

GOODBYE HARTMANN – AFTER 100 YEARS HARTMANN'S PROCEDURE IS GOING TO BE ABANDONED?

STUDY PROTOCOL WITH ICF - VERSION 2 09.03.2021

emergency surgical procedures; annual volume of left-sided colonic disease; types of diagnostic and treatment modalities that are available in the hospital.

- Treatment: Hartmann's procedure, colonic resection with primary anastomosis with or without diverting stoma, stoma without colic resection.
- Surgeon experience (surgeon in training: less than 50 colorectal resections performed; less than 5 resections per year in the last 5 years; Trained surgeon: more than 50 colorectal resections performed; more than 10 resections per year in the last 5 years)
- Time of surgery: weekdays, weekend, public holidays, night shift (day: 8am- 8pm; night: 8pm-8am)
- Postoperative course: Clavien-Dindo Classification; reoperation
- Follow-up: to evaluate the number of patients treated with Hartmann's procedure have a permanent stoma after one year.

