6. ANALYSIS

6.1 ANALYSIS STRATEGY

The first study objective is to investigate what factors contribute in the choice of Hartmann's procedure instead of colonic resection with primary anastomosis and what type of surgery is commonly performed in different level of care hospitals

Univariate analysis is performed on relevant parameters that are described in chapter 5.7- list of study parameters and 5.8-patient characteristics. Factors that are considered to be clinically relevant based on literature and/or expert opinion are selected for multivariate analysis.

Backwards selection is used to exclude values of $p > 0.05$ from the model.

The results obtained by the described analyses will also be performed in subgroups of patients who underwent Hartmann's procedure or primary anastomosis with or without diverting ileostomy. By performing this sensitivity analysis, we will investigate the factors behind the choice to perform Hartmann's procedure or colic resection with primary anastomosis.

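### The two surgeon-experience classes in section 5.7 cannot be both non-overlapping and complete, whichever way their criteria are joined

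*Protocol*

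**What the plan says.** Section 5.7 gives surgeon experience two classes. A surgeon in training has fewer than 50 colorectal resections, followed by a second criterion that runs straight into the next class: "less than 5 resections per year in the last 5 years; Trained surgeon: more than 50 colorectal resections performed". The trained class also has an annual criterion: "more than 10 resections per year in the last 5 years". Semicolons separate all four criteria. Neither *and* nor *or* appears, and no third class is given.

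The item is used in the analysis. The second bullet of section 3 lists, among the factors behind the choice of operation, "surgeon experience, time of surgery, age of patients, comorbidities, etc". Section 5.6 repeats surgeon experience as a secondary outcome parameter, and section 6.1 draws on the list in which it stands: "Univariate analysis is performed on relevant parameters that are described in chapter 5.7- list of study parameters and 5.8-patient characteristics".

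The rationale in section 2 gives the factor weight. It says of Hartmann's procedure that "This technique is often performed by young surgeons", and of operations outside normal hours that they take place "when maybe best colorectal expertise is lacking for decision making regarding anastomosis".

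Section 8.2 says that the case report form carries explanatory notes for scoring the listed parameters. That form is not part of the document at hand.

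**The concern.** A categorical factor can be analysed only if each surgeon falls into exactly one class. Here the annual cut-offs leave 5 to 10 uncovered, the lifetime cut-offs leave exactly 50 uncovered, and nothing says what to do when the lifetime and annual criteria point in different directions. An experienced surgeon who now does few resections is the plainest case of the last kind.

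Many sites in several countries will apply this definition. If they supply the missing connective differently, two surgeons with the same record get different codes. If they find that no class fits, the item may be left blank, and which patients lack it would then depend on surgeon volume, the characteristic under study. Either outcome weakens what the study can say about surgeon experience and the choice of Hartmann's procedure. If the database holds only the class, a later analysis plan cannot recover the counts.

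**Working it through.** There is no stated figure to reproduce. The check is a logical one on the four cut-offs in section 5.7.

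**Inputs.** Let T be lifetime colorectal resections and r the mean number a year over the last 5 years. Reading the annual criterion as a mean is my assumption.

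- In training: T < 50; r < 5.
- Trained: T > 50; r > 10.

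**Feasibility.** With a full 5-year record, T is at least 5r. Since 5 × 10 = 50, a rate above 10 a year implies T above 50. So r > 10 cannot occur together with T of 50 or less, and such pairs are left out below.

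**Four ways to join the criteria.**

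1. *And* in both classes. No overlap is possible. Unclassed: r from 5 to 10 at any T; T > 50 with r < 5; and T = 50.
2. *Or* in both classes. Every surgeon with T > 50 and r < 5 is in both classes. The only gap is T = 50 with r from 5 to 10.
3. In training by *or*, trained by *and*. No overlap. Unclassed: T of 50 or more with r from 5 to 10.
4. In training by *and*, trained by *or*. No overlap. Unclassed: T < 50 with r of 5 or more, and T = 50.

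**Example surgeons (T, r).**

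| T, r | 1: and/and | 2: or/or | 3: or/and | 4: and/or |
|---|---|---|---|---|
| 40, 3 | in training | in training | in training | in training |
| 40, 7 | none | in training | in training | none |
| 50, 7 | none | none | none | none |
| 200, 7 | none | trained | none | trained |
| 200, 3 | none | both | in training | trained |
| 200, 12 | trained | trained | trained | trained |

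Only the first and last rows are stable. The surgeon with 200 lifetime resections and 3 a year gets a different result under each of the four readings. No column gives every row exactly one class.

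The properties that fail differ by reading. Readings 1, 3 and 4 are exclusive but incomplete. Reading 2 overlaps over a wide range and is incomplete only at a single lifetime value.

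**The case against.** The strongest reply is that section 8.2 points to scoring notes in the case report form, which is where a coding rule would normally sit. This stands as a limit on the consequence: inconsistent coding or missing values are possible, not shown. It does not repair section 5.7, which states explicit cut-offs that do not work as written and would still have to match the form.

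A second reply is that a kinder reading shrinks the problem. Mixed connectives remove the overlap. Treating the lifetime and annual criteria as two separate items removes the conflict between them. That is fair, but the mixed readings keep the gaps shown above, and the separate-item reading still leaves exactly 50 lifetime and 5 to 10 a year without a place.

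A third reply is about weight. Surgeon experience is one of many candidate factors, and the primary outcome in section 5.5, the number of each procedure, does not depend on it. This stands.

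The protocol does not support three stronger inferences that a reader might draw:

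- *That most surgeons are affected.* Counting combinations of T and r suggests a large share, but such counts give the single value 50 as much room as whole ranges, and they are not frequencies. The protocol gives no distribution of surgeon volume.
- *That typical surgeons fall in the 5-to-10 gap.* Section 5.4 expects that "on average, three patients will undergo urgent left-sided colonic diseases resection per month at each participating centre", or 3 × 12 = 36 a year. Dividing this among surgeons proves nothing: it counts only urgent left-sided work, whereas the lifetime criterion counts all colorectal resections and the annual one is not limited to urgent work. The number of surgeons per centre is not given.
- *That the factor list is defective more widely.* Section 2 says that end-colostomy may be needed "because of unfavourable local conditions (Hinchey IV peritonitis"), yet sections 5.7 and 5.8 list no contamination grade. That is a separate question of covariates, and absence from the lists does not show that the grade goes uncollected.

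**Conclusion.** The point holds as a defect in a stated definition. None of the four ways of joining the criteria in section 5.7 yields two classes that are both exclusive and exhaustive. The cases left out or counted twice include unremarkable profiles, such as 200 lifetime resections with 7 or 3 a year, as well as the boundary value of 50.

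Its reach is limited to surgeon experience as a factor under the second objective and in the section 6.1 analysis. Whether it causes inconsistent or missing codes depends on the case report form, which cannot be checked here. It would be tempting to conclude that the estimated effect of surgeon experience will be biased; the protocol supports neither a size nor a direction for such a bias. The wording defect is certain, and its effect on the results is open.

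**What to change.** In section 5.7, record two numbers for the operating surgeon, both as of the operation: lifetime colorectal resections, and mean annual resections over the last 5 years. From these, define one exhaustive, non-overlapping set of classes that assigns exactly 50, assigns 5 to 10 a year, and states a rule for surgeons whose lifetime and annual counts disagree. One way that keeps the present cut-offs is to require both criteria for each existing class and to put everyone else in a named third class. If the case report form already contains a complete rule, it is enough to align section 5.7 with it.

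For new entries, the cost is a change of wording and two numeric fields, and surgeons will have to estimate their counts. For patients already entered, the cost is higher. Sections 5.7 and 5.8 list no surgeon identifier, so sites would have to link each patient to the operator through the local files described in section 8.4. Section 8.3 says that no dates are collected, so each site would also have to date the counts to the operation from its own records. Counts supplied during the March to May 2022 follow-up must not be taken as of that time, because a surgeon may have passed 50 in the meantime.

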5.8 PATIENT CHARACTERISTICS

- Age
- Sex
- Weight
- Previous abdominal surgery
- Charlson comorbidity index
- ASA classification
- Clinical status: stable patient; unstable patient; sepsis (qSOFA score)

6. ANALYSIS

6.1 ANALYSIS STRATEGY

The first study objective is to investigate what factors contribute in the choice of Hartmann's procedure instead of colonic resection with primary anastomosis and what type of surgery is commonly performed in different level of care hospitals

Univariate analysis is performed on relevant parameters that are described in chapter 5.7- list of study parameters and 5.8-patient characteristics. Factors that are considered to be clinically relevant based on literature and/or expert opinion are selected for multivariate analysis.

Backwards selection is used to exclude values of $p > 0.05$ from the model.

The results obtained by the described analyses will also be performed in subgroups of patients who underwent Hartmann's procedure or primary anastomosis with or without diverting ileostomy. By performing this sensitivity analysis, we will investigate the factors behind the choice to perform Hartmann's procedure or colic resection with primary anastomosis.

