should be preferred for uncomplicated malignant left-sided large bowel obstruction in absence of other risk factors. Patients with high surgical risk are better managed with Hartmann's procedure

Despite the growing evidence in favour of primary anastomosis and its inclusion as a valid treatment option for perforated diverticulitis or perforated sigmoid colon in recent clinical practice guidelines, some surgeons have been hesitant to undertake anastomosis in the setting of purulent or faecal contamination and continue to choose Hartmann's procedure to eliminate concerns about anastomotic leakage.

Primary study objective:

GOODBYE HARTMANN – AFTER 100 YEARS HARTMANN'S PROCEDURE IS GOING TO BE ABANDONED?

STUDY PROTOCOL WITH ICF - VERSION 2 09.03.2021

1. To evaluate the role of Hartmann's procedure in emergency setting for left-sided colonic acute surgical disease (perforated diverticulitis with purulent or fecal peritonitis; colon cancer perforation-occlusion; ischemic colitis; abdominal trauma) and the type of surgery commonly performed in different level of care hospitals.
2. To investigate which factors contribute in the choice of Hartmann's procedure instead of colon resection with primary anastomosis (Hospital characteristics, surgeon experience, time of surgery, age of patients, comorbidities, etc)

Study design: International multicenter prospective cohort study.

Study population: Adult patients with left-sided colonic acute surgical disease who need surgery in an emergency setting (perforated diverticulitis with purulent or fecal peritonitis; colon cancer perforation-occlusion; ischemic colitis; abdominal trauma). All patients undergoing urgent surgery will be invited to participate and can choose to consent or decline

Primary outcome: Hartmann's procedure vs colonic resection with primary anastomosis performed in a 3-months interval in an emergency setting for left-sided acute surgical colonic diseases.

Secondary outcomes: risk factors for Hartmann procedure (Hospital characteristics (secondary, tertiary level, trauma center), surgeon experience, time of surgery (day of surgery- weekend; day or night), patient's age, comorbidities, clinical status etc.

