4. STUDY DESIGN

4.1 STUDY TYPE

International multicenter prospective cohort study.

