4.2 DURATION OF THE STUDY

Data from 3 months cohort of patients who underwent urgent or emergency Hartmann’s procedure, resection with primary anastomosis for left-sided colonic disease from March 1st 2021 until May 31st 2021 will be recorded with one-year follow-up from surgery until May 2022. The total study duration will be from January 2021 until December 2022(22 months).

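### Section 6.1 tests hospital-level factors without accounting for centre, so their intervals are too narrow and backward elimination keeps them too often if choice of procedure is correlated within centres

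*Protocol*

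**What the plan says.** The study is described in section 4.1 as an "International multicenter prospective cohort study". Its second primary objective (section 1, repeated in section 3) asks which factors lead to Hartmann's procedure rather than primary anastomosis, and gives as examples "Hospital characteristics, surgeon experience, time of surgery, age of patients, comorbidities, etc". The first objective includes the type of surgery by hospital level of care.

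Section 6.1 sets the route: "Univariate analysis is performed on relevant parameters that are described in chapter 5.7- list of study parameters and 5.8-patient characteristics". Factors judged clinically relevant then enter a multivariate analysis, and backward selection removes those with p > 0.05. Section 5.7 lists the hospital characteristics: hospital type, two annual volumes, and "types of diagnostic and treatment modalities that are available in the hospital".

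Section 5.4 expects that "three patients will undergo urgent left-sided colonic diseases resection per month at each participating centre". It says nothing about correlation between patients of the same centre. No section mentions a centre or surgeon effect, a random intercept, GEE, robust variance or stratification by centre.

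**The concern.** Hospital type, annual volume and available modalities do not vary between patients of one centre. For these factors the independent units are the centres. An analysis that treats each patient as a separate observation of the hospital takes its precision from the number of patients instead.

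This matters if two patients of the same centre are more alike in the procedure they receive than two patients of different centres, after the factors in the model are allowed for. Section 2 names surgeons' reluctance, legal concerns and the lack of colorectal expertise outside working hours as reasons for choosing Hartmann's procedure. Such influences may well be shared within a hospital, although the protocol does not say so.

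Hospital factors are exposures of interest under a primary objective. The p > 0.05 rule acts directly on their p-values, so understated standard errors would decide which hospital factors stay in the final model as well as how precise they look.

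**Working it through.** **The plan's own figure.** Section 5.4 says: "Applying root mean square percentage error (rMSPE) of 15%, 500 patients treated with left colon resection with or without primary anastomosis should be included". This 500 cannot be rebuilt, because no outcome proportion, number of predictors, effect size, power or ICC is given. Three readings of the 15% (absolute 95% half-width, relative 95% half-width, relative standard error), for proportions of 0.3 to 0.7, give about 19 to 398 patients and never 500. The derivation of 500 is a separate matter; here it is taken as given.

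**Inputs from the protocol**
- Patients per centre per month: 3 on average (section 5.4).
- Accrual: 3 months, "from March 1st 2021 until May 31st 2021 will be recorded with one-year follow-up" (section 4.2).
- Total: "Therefore, the aim is to include at least 500 patients" (section 5.4).
- Retention threshold: 0.05 (section 6.1; sidedness not stated, two-sided assumed).

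**Assumed:** the residual ICC, at 0.02, 0.05, 0.10 and 0.20. The protocol supports no particular value.

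**Cluster size.** m = 3 × 3 = 9. Centres = 500 / 9 = 55.6, about 56.

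**Formulas for a factor constant within a centre**
- Design effect: DE = 1 + (m − 1) × ICC = 1 + 8 × ICC
- Correct standard error / naive standard error = √DE
- Effective number of patients = 500 / DE
- Actual error of a nominal 5% test = 2 × [1 − Φ(1.96 / √DE)]

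| ICC | DE | SE ratio | Effective N | Actual error |
|---|---|---|---|---|
| 0 | 1.00 | 1.00 | 500 | 5.0% |
| 0.02 | 1.16 | 1.08 | 431 | 6.9% |
| 0.05 | 1.40 | 1.18 | 357 | 9.8% |
| 0.10 | 1.80 | 1.34 | 278 | 14.4% |
| 0.20 | 2.60 | 1.61 | 192 | 22.4% |

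**Simulation check.** The set-up was 56 centres, a normal random intercept for centre on the logit scale, a factor with no effect, an ordinary two-proportion test at 5%, and 1,500 runs per cell (Monte Carlo standard error about 0.6 points near 5%).

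| ICC (logit scale) | Site factor, 9 per centre | Site factor, unequal centres averaging about 9 | Surgeon experience, mix varies by centre | Surgeon experience, balanced within centres |
|---|---|---|---|---|
| 0 | 4.8% | 6.1% | 4.5% | 5.3% |
| 0.05 | 8.8% | 10.4% | 6.4% | 4.9% |
| 0.10 | 12.6% | 17.6% | 8.7% | 5.7% |
| 0.20 | 19.9% | 25.9% | 15.5% | 3.6% |

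With equal centres the simulated errors lie a little below the formula. One reason is that a given ICC on the logit scale is a smaller correlation on the scale of proportions. Unequal centres push the error up.

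The surgeon columns assume a centre effect only, and the mixed case assumes three surgeons per centre. A surgeon's own habit would add correlation where one surgeon treats several patients. That is not quantified, because the protocol gives no number of patients per surgeon.

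**The case against.** **Silence is not a stated choice.** Section 6.1 names no model and no variance estimator, and does not say that centre is ignored. A statistical analysis plan, if one exists, could add a centre effect, and modelling detail of that kind is often left to it. This stands as a limit on the wording: a reader might infer that the protocol prescribes an analysis ignoring centre, and it does not. It does not remove the point. The protocol itself fixes the sequence of analyses and the p-value that decides retention, applies them to factors constant within centres, and gives centre no role.

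**The size is conditional.** This stands. No ICC is given, and at zero there is no inflation. What counts in the multivariate model is the correlation left after its factors are included, since centre differences that those factors explain are the signal sought.

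**Nine per centre is an expected average.** This also stands. Patients may decline, exclusions apply, and centres received documents in March 2021 and may then have needed local approval. With 5 per centre and ICC 0.05, DE = 1 + 4 × 0.05 = 1.2 and the error is about 7.4%. Unequal centre sizes work in the other direction.

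**Surgeon factors.** A reader might infer that surgeon experience is affected as firmly as hospital type. The documents do not support that. If experience is balanced within centres, the centre effect causes no inflation.

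**Patient factors.** A reader might also infer that accounting for centre would remove between-centre case-mix from the patient-factor estimates. It would not. GEE and cluster-robust variance do not isolate within-centre effects, and a random intercept mixes within-centre and between-centre information.

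**The primary outcome.** The number of Hartmann's procedures against primary anastomoses (section 5.5) is not biased by this. The point concerns inference on factors.

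**Conclusion.** The point holds for hospital-level factors. Followed as written, section 6.1 understates their standard errors, and its p > 0.05 rule retains them too often, provided that choice of procedure is correlated within centres beyond what the model explains.

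Under the assumed residual ICCs and about 9 patients per centre, the consequence runs from minor (6.9% error at ICC 0.02) through material (9.8% at 0.05) to serious (22.4% at 0.20). These figures illustrate the range and do not estimate what the study will show.

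For surgeon experience the effect is smaller and arises only if experience varies between centres or surgeons contribute several patients. The weakness should be corrected because it touches a primary objective and the remedy is simple. It does not undermine the study as a whole.

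**What to change.** Add to section 6.1 that the univariate and multivariate models of Hartmann's procedure versus primary anastomosis account for centre. This can be a logistic model with a random intercept for centre, or GEE or cluster-robust variance by centre. State that backward elimination at p > 0.05 uses the p-values from those models. Name one method in advance, because the random intercept gives centre-specific odds ratios and the others population-averaged ones.

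The change is one of analysis wording. Site logins (section 8.1) and the restriction of each centre to its own data (section 8.4) imply that the database identifies the centre, so no new data should be needed. The downside is wider intervals for hospital factors, and some may no longer be retained. Reporting the between-centre variation in the share of Hartmann's procedures would be informative but is optional.

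### Section 6.1 lets time of surgery be adjusted for surgeon experience and then pruned at p > 0.05, so no off-hours estimate adjusted for the patient but not for the surgeon is planned

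*Protocol*

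**What the plan says.** Protocol section 3 (Study objectives) asks which factors contribute to choosing Hartmann's procedure over resection with primary anastomosis, and lists them side by side: "Hospital characteristics, surgeon experience, time of surgery, age of patients, comorbidities, etc". Section 5.7 defines the two that matter here: "Time of surgery: weekdays, weekend, public holidays, night shift (day: 8am- 8pm; night: 8pm-8am") and "Surgeon experience (surgeon in training: less than 50 colorectal resections performed", with further volume limits for the trained category.

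Section 6.1 describes the analysis in three steps:
- **Univariate step:** "Univariate analysis is performed on relevant parameters that are described in chapter 5.7- list of study parameters and 5.8-patient characteristics".
- **Entry to the model:** "Factors that are considered to be clinically relevant based on literature and/or expert opinion are selected for multivariate analysis".
- **Removal:** "Backwards selection is used to exclude values of" p > 0.05 from the model.

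It names no variable that must enter or stay, and does not say whether a coefficient is meant as an overall effect or as one conditional on the other factors.

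Section 2 (Introduction and rationale) links timing to expertise, remarking that "most of these procedures are performed off normal working hours when maybe best colorectal expertise is lacking for decision making regarding anastomosis".

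**The concern.** The Introduction sketches a possible chain from off-hours surgery, through less expertise at hand, to Hartmann's procedure. If recorded surgeon experience captures part of that chain, it is an intermediate step for time of surgery rather than a confounder. Putting both in one model changes what the timing coefficient means: it becomes the association of off-hours surgery with Hartmann's among operations done by surgeons of the same experience. The part that works through who operates is taken out.

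Backward selection adds a second problem, because p-values then decide which quantity is reported. If surgeon experience is dropped first, timing shows its effect with the surgeon pathway included. If surgeon experience stays, timing shows only the remainder, and a remainder that misses p ≤ 0.05 is removed. The study could then report that timing does not contribute to the choice, although the Introduction's own explanation was correct.

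**Working it through.** **1. What the plan yields for timing.** Section 6.1 gives two kinds of timing estimate. One is univariate, adjusted for nothing. The other is multivariate, adjusted for whatever enters and survives. An estimate adjusted for clinical status, qSOFA, ASA, comorbidity (section 5.8) and etiology (section 5.7), but not for the surgeon, is not specified.

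**2. The plan's own figures.** None can be reproduced on this point. The protocol gives no proportion of Hartmann's procedures, no off-hours share, no surgeon mix and no effect size. Only the target of 500 patients (section 5.4) is used below; every other input is an assumption.

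**3. Overall odds ratio when the whole effect runs through the surgeon.** Let *h*_T and *h*_L be the probabilities of Hartmann's with a trained and a less experienced surgeon, and *s* the share of less experienced surgeons in a period. Then

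*p* = (1 − *s*)·*h*_T + *s*·*h*_L.

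Assume *h*_T = 0.40, *s* = 0.20 by day and 0.55 off-hours, and a surgeon odds ratio of 3.
- Odds for a less experienced surgeon: (0.40/0.60) × 3 = 2, so *h*_L = 2/3.
- Day: 0.80 × 0.40 + 0.20 × 0.667 = 0.453.
- Off-hours: 0.45 × 0.40 + 0.55 × 0.667 = 0.547.
- Overall odds ratio: (0.547/0.453) / (0.453/0.547) = 1.45.

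With surgeon odds ratios of 2 and 5 the overall odds ratio is 1.27 and 1.69. Within each surgeon group the day and off-hours probabilities are equal, so the adjusted odds ratio is 1.00 by construction.

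In 1,500 simulated studies of 500 patients per scenario (55% off-hours), timing reaches p ≤ 0.05 without surgeon experience in the model in 28%, 53% and 82% of studies for surgeon odds ratios of 2, 3 and 5. With surgeon experience in the model the figure is about 5% throughout.

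**4. Relaxing complete mediation and applying the removal rule.** These are separate simulations: n = 500, 1,500 runs per row, 50% off-hours, and two candidate variables reduced by backward removal at p > 0.05. The log-odds of Hartmann's are −0.25·ln(OR_surgeon) + ln(OR_surgeon)·(less experienced) + ln(OR_direct)·(off-hours).

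| Less experienced, day / off-hours | Surgeon OR | Direct timing OR | Timing OR without surgeon | Timing OR with surgeon | p < 0.05 without surgeon | Timing kept after selection |
|---|---|---|---|---|---|---|
| 30% / 60% | 3 | 1.0 | 1.39 | 1.00 | 44% | 5% |
| 20% / 70% | 3 | 1.0 | 1.73 | 1.00 | 86% | 5% |
| 30% / 60% | 3 | 1.5 | 2.00 | 1.49 | 97% | 52% |
| 20% / 70% | 3 | 1.5 | 2.50 | 1.50 | 100% | 46% |
| 40% / 50% | 2 | 1.5 | 1.59 | 1.51 | 72% | 59% |
| 30% / 60% | 2 | 2.0 | 2.40 | 1.99 | 99% | 94% |

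**5. Reading the table.** With no direct effect, the plan would nearly always drop timing. With a direct odds ratio of 1.5, timing is attenuated and lost in 41% to 54% of runs (100% − 59% and 100% − 46%). With weak mediation (fifth row) or a strong direct effect (last row) the loss is much smaller. The simulations contain no patient confounders, so here the estimate without the surgeon is also the univariate one. In the real study the two would differ wherever off-hours patients are sicker or have different etiologies.

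**The case against.** Several counter-arguments have force and limit the point.

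- **Section 6.1 names no variables.** A reader might infer that it puts timing and surgeon experience in one model. It only lets them enter, and a covariate list may sit in a statistical analysis plan that is not shown. This stands as a limit on wording. But both factors are named in the objective, so leaving either out would leave that factor without an adjusted answer. The entry and removal rules are also fixed in the protocol itself.
- **The mechanism is hedged and imperfectly measured.** The Introduction says "most of these procedures are performed off normal working hours when maybe best colorectal expertise is lacking for decision making regarding anastomosis", which is a possibility and not a causal model. The recorded variable is the surgeon's own resection volume, only a proxy for expertise available for the decision. A reader might infer that the off-hours effect is adjusted away altogether. The text does not support that: attenuation is the general result, and 1.00 follows only from assuming no direct effect.
- **The univariate step already reports timing without the surgeon.** It does, and a careful author would notice a crude association that vanishes on adjustment. But that estimate cannot separate off-hours staffing from sicker off-hours patients.
- **Independent association is a legitimate reading of the objective.** True. The protocol does not say which effect it means, so the conditional estimate is worth reporting. It should not be the only adjusted one.
- **Hospital level.** A reader might extend the argument to hospital level. No passage says that it acts through surgeon experience. The objective concerning "the type of surgery commonly performed in different level of care hospitals" is descriptive and can be answered by counts. Hospital level precedes both timing and surgeon, so it is a plausible confounder to adjust for. The extension is not made here.

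**Conclusion.** The concern holds for time of surgery only. If time of surgery and surgeon experience both enter the section 6.1 model, the timing coefficient is the part not carried by measured surgeon experience, and the p > 0.05 rule may delete it. No planned estimate gives the off-hours effect adjusted for the patient and not for the surgeon.

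The size depends on assumptions that the protocol does not supply. Timing is kept in about 5% of simulated studies under complete mediation, in 46% to 59% with a direct odds ratio of 1.5, and in 94% with a direct odds ratio of 2 and a surgeon odds ratio of 2. Part of the loss in the middle range is limited power at 500 patients for a direct odds ratio of 1.5, not attenuation alone. The change is worth making because the factor is named in the objective and the remedy needs no new data. The documents do not show that the effect would vanish.

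**What to change.** In section 6.1, prespecify two models for time of surgery.

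1. **Overall timing model.** Time of surgery adjusted for patient characteristics, etiology and hospital characteristics, without surgeon experience. Time of surgery is exempt from backward selection and reported with its confidence interval whatever its p-value. The overall timing answer comes from this model.
2. **Surgeon model.** The same model with surgeon experience added. It gives the surgeon-experience answer, and the timing estimate conditional on the surgeon.

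State that the difference between the two timing estimates is described only, and not reported as a proportion explained. Odds ratios change when a covariate is added even without mediation, and unmeasured factors may affect both who operates and which procedure is chosen.

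The cost is a few sentences of analysis text and one more model and table to explain. All variables are already collected, and no patients are added.
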